#### **9.4.3. Laboratory Tests**

##### **9.4.3.2 Laboratory Tests for Patients at Sites in Japan**

Beta-D-glucan levels and KL-6 levels (biomarkers for PCP and interstitial lung disease, respectively) will be measured at screening and, if an investigator believes it is warranted, at subsequent visits. Either test may be included in the work up panel at any time during the study, including in the follow-up period.

If the beta-D-glucan test is positive, PCP needs to be ruled out. If PCP is ruled out and the investigator deems the patient fit to continue, the patient may continue in the study. If a patient has a confirmed diagnosis of PCP during the study, the patient must discontinue the study.

##### **9.4.5.3. Chest Radiography**

Posterior-anterior (PA) chest x-ray (CXR) will be obtained at screening (Visit 1) unless, in the opinion of the investigator or based on local standard of care, both PA and lateral views are indicated. In addition, chest radiography will be performed at Week 52, or for subjects who discontinue the study early if more than 12 weeks have elapsed since the previous study radiography was obtained. If medically indicated, this radiography may be performed even when 12 weeks have not elapsed since the previous study radiography. Chest radiography may be performed at any time during the study, including the follow-up period, if medically necessary in the opinion of the investigator.

A CXR does not have to be performed if the patient has had a CXR that is sufficient for TB evaluation according to local standard of care within 3 months of screening, and the CXR film(s) or a radiology report is available to the investigator for review.

##### **9.4.5.4. Hepatitis B Screening**

Patients who test HBsAg+, test HBcAb+ in conjunction with positive confirmatory HBV DNA test, or have positive HBV DNA test, regardless of HBsAb status, at screening will be excluded.

Any enrolled subject who is HBcAb+ and/or HBsAb+ will undergo periodic monitoring of HBV DNA per the Schedule of Activities (Section 2).

In addition to the above, any enrolled subject who is HBcAb+ and/or HBsAb+ and who experiences an elevated ALT or AST level  $>3 \times$  ULN must undergo HBV DNA testing. If the HBV DNA test is negative, the investigator should consult with the Lilly-designated medical monitor regarding further management of the patient.

If the result of the HBV DNA test is positive but below quantification study drug should be withheld and a repeat test done immediately. The Lilly-designated medical monitor should be contacted regarding study status of the patient. If the result of the HBV DNA test is DNA positive and quantifiable, the patient must be discontinued from the study and should receive appropriate follow-up medical care, including consideration for antiviral therapy. A specialist physician in the care of patients with hepatitis (for example, infectious disease or hepatologist subspecialists) should be consulted, and the patient should potentially be started on antiviral therapy prior to discontinuation of any immunosuppressant therapy (including study drug). Timing of discontinuation from the study treatment, the study, and of any immunosuppressant therapy (including study drug) needs to be based on the recommendations of the consulting specialist physician in conjunction with the investigator and medical guidelines/standard of care.

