### 6.2. Exclusion Criteria

- [13] Have hepatitis B or test positive for hepatitis B virus (HBV) at screening, defined as:
- A. Positive for hepatitis B surface antigen (HBsAg+),  
OR
  - B. Positive for hepatitis B core antibody (HBcAb+) in conjunction with positive confirmatory HBV for HBV deoxyribonucleic acid (DNA) test,  
OR
  - C. ~~Positive HBV DNA, regardless of anti-hepatitis B surface antibody (HBsAb) status.~~ Positive for hepatitis B surface antibody (HBsAb+) and positive confirmatory for HBV DNA

Note: Patients who are HBcAb+ and/or HBsAb+ and HBV DNA negative may be enrolled in the study. Patients who meet these criteria at screening will be monitored during the study as detailed in revised protocol Section 9.4.5.4 (Section 4.7 of this addendum).

- [16] Have had serious, opportunistic (see Section 9.2.3 and Appendix 4), or chronic/recurring infection (including pneumocystis pneumonia [PCP]) within 3 months prior to screening. Examples include, but are not limited to, infections requiring IV antibiotics, hospitalization, or prolonged treatment.
- [23] Have any other skin conditions (excluding plaque psoriasis, pustular psoriasis, and erythrodermic psoriasis) that would affect interpretation of the results (including, but not limited to, scleroderma, eczema, drug-induced psoriasis, guttate psoriasis, ~~pustular psoriasis~~, parapsoriasis, or cutaneous manifestations of other autoimmune diseases such as systemic lupus erythematosus).

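### Revised exclusion criterion 13 and revised Section 9.4.5.4 of the Japan addendum give opposite answers for one hepatitis B profile: negative for HBsAg and both antibodies, but HBV DNA positive

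*Protocol*

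**What the plan says.** Section 4 of the addendum explains that underlined and struck text marks the changes for patients in Japan. Both provisions below belong to that current text.

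- **Section 4.4, revised Section 6.2, criterion 13.** The stem is "Have hepatitis B or test positive for hepatitis B virus (HBV) at screening, defined as", followed by three limbs joined by OR. Limb A is a positive HBsAg. Limb B is "Positive for hepatitis B core antibody (HBcAb+) in conjunction with positive confirmatory HBV for HBV deoxyribonucleic acid (DNA) test". In limb C the words "Positive HBV DNA, regardless of anti-hepatitis B surface antibody (HBsAb) status" are struck out and replaced by "Positive for hepatitis B surface antibody (HBsAb+) and positive confirmatory for HBV DNA".
- **Note under criterion 13.** "Patients who are HBcAb+ and/or HBsAb+ and HBV DNA negative may be enrolled in the study". It refers to revised Section 9.4.5.4 for the monitoring of these patients. It does not mention antibody-negative, DNA-positive patients or say which exclusion definition governs.
- **Section 4.7, revised Section 9.4.5.4.** The exclusion sentence begins "Patients who test HBsAg+, test HBcAb+ in conjunction with positive confirmatory HBV DNA test, or" and ends "have positive HBV DNA test, regardless of HBsAb status, at screening will be excluded". The same section limits periodic HBV DNA monitoring, and the HBV DNA test triggered by ALT or AST above 3 times ULN, to enrolled patients who are HBcAb+ and/or HBsAb+.
- **Discontinuation.** The Rationale (Section 3) and footnote n to the Schedule of Activities (Section 4.1) both call for discontinuation after any positive HBV DNA test during the study.

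**The concern.** Both provisions decide who may enter the study, and both are stated as rules. The limb that criterion 13 deletes survives in Section 9.4.5.4, so a site that consults one place can reach a different eligibility decision from a site that consults the other.

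What is at stake is patient safety, not inference. The patient on whom the rules disagree has a positive viral DNA test and no HBV antibody. Later HBV DNA testing in the addendum is tied to antibody status, so if this patient were enrolled under criterion 13, neither the periodic nor the enzyme-triggered testing would apply.

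**Working it through.** No sample size, power or error rate is involved. The check is a logical comparison of the two rules.

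**Inputs.** Four screening markers, each positive or negative: HBsAg, HBcAb, HBsAb and HBV DNA. That gives 2 × 2 × 2 × 2 = 16 combinations.

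**Rules.**
- Criterion 13 (Section 6.2): HBsAg OR (HBcAb AND DNA) OR (HBsAb AND DNA).
- Section 9.4.5.4: HBsAg OR (HBcAb AND DNA) OR DNA. The middle limb is contained in the last, so this reduces to HBsAg OR DNA.

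**Comparison.**

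| Profile | Combinations | Criterion 13 | Section 9.4.5.4 |
|---|---|---|---|
| HBsAg+ (any other results) | 8 | excluded | excluded |
| HBsAg-, DNA- (any antibodies) | 4 | not excluded | not excluded |
| HBsAg-, DNA+, at least one of HBcAb and HBsAb positive | 3 | excluded | excluded |
| HBsAg-, DNA+, HBcAb-, HBsAb- | 1 | **not excluded** | **excluded** |

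The rules agree in 8 + 4 + 3 = 15 of 16 combinations and disagree in 1. HBsAg negativity is part of the discordant profile: an antibody-negative, DNA-positive patient who is HBsAg+ is excluded by both.

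**Can other text close the gap?**
- The general opening words of criterion 13 do not, because the stem goes on to define them by limbs A to C.
- The note under criterion 13 does not, because it covers only antibody-positive, DNA-negative patients.

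**What would follow for the discordant patient?**
- Under Section 9.4.5.4 the patient never enters, so no monitoring question arises.
- Under criterion 13 alone the patient could enter. Antibody-based monitoring would not apply, although footnote n would still call for discontinuation on a positive DNA test.

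**Would the DNA result be known?** The Schedule of Activities marks HBV DNA testing at screening but does not clearly say who is tested, and criterion 13 calls the DNA test confirmatory.
- If only antibody-positive patients are tested, this patient has no DNA result and neither rule acts on it.
- If everyone is tested, the result is known and the two rules give opposite answers.

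**The case against.** The strongest reply is that the harm is remote.

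- **Other text catches the patient.** Section 9.4.5.4 is current text and excludes this patient at screening. If the patient were enrolled, the Rationale and footnote n call for discontinuation. A reader might infer that the plan admits a viraemic patient to an immunomodulator and then leaves that patient unfollowed. The documents do not support this: nothing in them says eligibility is run from the exclusion list alone, and admitting and keeping a patient known to be DNA positive would mean disregarding all three of these places. This part of the objection stands and limits the size of the point. It does not remove the conflict, because discontinuation is not an eligibility rule. The backstop is also not uniform: Section 9.4.5.4 treats a positive result below quantification differently (withhold, repeat, contact the medical monitor), and the addition to Section 8.2 shown in addendum Section 4.6 lists only pneumocystis pneumonia.
- **The DNA test may be run only after a positive antibody.** In that case aligning the two definitions would change nothing for this patient. This also stands as a limit. The main protocol, which may settle who is tested, is not among the documents.
- **A strikethrough may have been lost from Section 9.4.5.4 when the PDF was read.** Edit marks do seem to be lost elsewhere: in Attachment 2 the old and new BSA thresholds for erythrodermic psoriasis run together unmarked. For Section 9.4.5.4 this remains speculation. A lost deletion would be expected to leave replacement wording beside it, as in criterion 13C, and there is none.

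**Conclusion.** The inconsistency is real and minor. Two current eligibility provisions in the addendum give opposite answers for exactly one of 16 marker profiles: HBsAg-, HBcAb-, HBsAb-, HBV DNA+. The documents do not give the frequency of that profile, so no number of affected patients can be stated. The point concerns only patients in Japan, to whom the addendum applies. No endpoint, estimand or statistical result depends on it.

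The conclusion rests on two assumptions: that the exclusion sentence in Section 9.4.5.4 is live text, as it reads, and that the main protocol does not say which definition prevails. Its practical reach further depends on whether antibody-negative patients have an HBV DNA test at screening, which the documents leave open.

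**What to change.** Reconcile criterion 13 and Section 9.4.5.4 so that both carry one hepatitis B exclusion definition. Which definition applies is the sponsor's clinical decision, and none is proposed here.

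In the same edit, state which patients have HBV DNA tested at screening, and check that this group and the group followed by periodic and ALT/AST-triggered HBV DNA testing match the chosen definition.

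The cost is about one sentence in the addendum, plus a short clarification of the screening test if the check shows that one is needed. No analysis, sample size or data collection for the efficacy endpoints changes.

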## 4.8. Section 10: Statistical Considerations

### 10.1. Sample Size Determination

In Cohort 1 (patients with plaque psoriasis), approximately 1443 patients will be randomized at a 4:4:4:1 ratio in the Blinded Induction Period to receive 250 mg mirikizumab SC at Weeks 0, 4, 8, and 12, then 250 mg mirikizumab SC Q8W, 250 mg mirikizumab SC at Weeks 0, 4, 8, and 12, then 125 mg mirikizumab SC Q8W, 300 mg secukinumab Q4W, or placebo. Stratified block randomization will be performed with the following stratification factors: previous exposure to biologic therapy (yes/no), body weight ( $<100$  kg or  $\geq 100$  kg), and geographic region (North America, Europe or Other).

Eight patients with GPP and 8 patients with EP will be enrolled in Cohort 2 in Japan. All patients in Cohort 2 will receive 250 mg mirikizumab SC at Weeks 0, 4, 8, and 12 during the Induction Period. During the Maintenance Period, starting at Week 16, GPP and EP patients will receive 250 mg mirikizumab Q8W SC for up to a total of 52 weeks. The number of patients with GPP and EP is based on the population size of these patients being very small in Japan (Umezawa et al. 2003, Rosenbach et al. 2010).

#### 10.3.1. General Statistical Considerations

The benefit/risk profile to support global registrations will be based on the analysis of Cohort 1.

Patients enrolled in Cohort 2 will not be included in the analysis supporting global registrations. To support registration in Japan, efficacy and safety analysis for plaque psoriasis, GPP, and EP

will be conducted separately. Safety data for all patients (plaque psoriasis, GPP, EP) will also be assessed.

**10.3.8. Interim Analyses**

In addition, the sponsor may consider interim analyses of Cohort 2 for Japan regulatory communication purposes. In this case, collected data may be summarized.

## Attachment 1. Protocol Addendum AMAJ(1) Clinical Laboratory Tests

---

In addition to the clinical laboratory tests included on Appendix 2 of the protocol, the following laboratory tests are required under this addendum:

---

### Clinical Chemistry

#### Serum Concentrations of:

Beta-D-glucan

KL-6

#### Other

HBV DNA testc

---

- c Following screening, patients will not undergo monitoring for Hepatitis C unless liver enzymes are elevated. Hepatitis B monitoring will be performed at protocol-specified intervals in patients who test positive for anti-hepatitis B core antibody and/or positive for anti-hepatitis B surface antibody.

---

## Attachment 2. Protocol Addendum Revisions

---

### Overview

Protocol Addendum I6T-MC-AMAJ(1) [A Multicenter, Randomized, Double-Blind, Placebo-Controlled Study Comparing the Efficacy and Safety of Mirikizumab to Secukinumab and Placebo in Patients with Moderate-to-Severe Plaque Psoriasis] has been amended due to trial site requests regarding concomitant medication. The revised protocol addendum is indicated by revision (1.1) and will be used in place of any preceding version of this protocol addendum.

The overall change made to this protocol addendum is as follows:

- Methotrexate or oral retinoids is permitted in addition to oral corticosteroids and cyclosporine

## Revised Protocol Addendum

**Note:** Deletions have been identified by ~~strikethroughs~~.  
 Addition to I6T-MC-AMAJ Clinical Protocol have been identified by the use of underscore.  
 Changes to I6T-MC-AMAJ (1.1) Clinical Protocol Addendum have been identified by the use of double underscore.

### Section number was arranged.

- |          |      |   |
|----------|------|---|
| [Before] | 4.5. | Section 8.2: Discontinuation from the Study |
|          | 4.6. | Section 7.7: Concomitant Therapy            |
| [After]  | 4.5. | Section 7.7: Concomitant Therapy            |
|          | 4.6. | Section 8.2: Discontinuation from the Study |

## 4.2. Section 4: Objectives and Endpoints

**Table AMAJ(1).1. Objectives and Endpoints**

To assess the efficacy of mirikizumab in patients with EP
	
EP ONLY
 
Time course of response to treatment as measured by the following measures:
 
 
• global improvement score
 
• change from baseline in PASI
 
• change from baseline in DLQI total score
 
 
At Week 16 and Week 52:
 
 
• global improvement score
 
• change from baseline in PASI
 
• change from baseline in DLQI total score
 

---	--

## 4.3. Section 5: Study Design

In parallel, the AMAJ(1) addendum will enroll Japanese patients who are diagnosed as GPP by the Japanese Dermatological Association or EP who have  $\geq 10$ 80% body surface area (BSA) involvement (with inflammatory erythema) (Cohort 2). Approximately 8 patients with GPP and 8 patients with EP will be enrolled in Cohort 2 in Japan.

## 4.4. Section 6: Study Population

## 6.2. Exclusion Criteria

Have hepatitis B or test positive for hepatitis B virus (HBV) at screening, defined as:

- A. Positive for hepatitis B surface antigen (HBsAg+),  
OR
- B. Positive for hepatitis B core antibody (HBcAb+) in conjunction with positive confirmatory HBV for HBV deoxyribonucleic acid (DNA) test,  
OR
- C. ~~Positive HBV DNA, regardless of anti-hepatitis B surface antibody (HBsAb) status.~~ Positive for hepatitis B surface antibody (HBsAb+) and positive confirmatory for HBV DNA

Note: Patients who are HBcAb+ and/or HBsAb+ and HBV DNA negative may be enrolled in the study. Patients who meet these criteria at screening will be monitored during the study as detailed in revised protocol Section 9.4.5.4 (Section 4.7 of this addendum).

## Prior/Concomitant Therapy

[24] Have received systemic nonbiologic therapy (including, but not limited to, oral psoralen plus ultraviolet A [PUVA] light therapy; cyclosporine; corticosteroids; methotrexate; oral retinoids; apremilast; tofacitinib; mycophenolate mofetil; thioguanine; hydroxyurea; sirolimus; tacrolimus; azathioprine; leflunomide; fumaric acid derivatives; or 1, 25 dihydroxy vitamin D3 and analogues) or phototherapy (including either oral and topical PUVA light therapy, ultraviolet B, excimer laser, or self treatment with tanning beds or therapeutic sunbathing) within 28 days prior to baseline.

[24a] GPP/EP ONLY:

- Methotrexate or oral retinoids will be permitted before and during the study if doses are not greater than that of baseline.
- Oral corticosteroids will be permitted before and during the study, if average daily doses are not greater than 10 mg/day of prednisone or its equivalent.
- Cyclosporine will be permitted until Week 2 (Visit 4), if daily doses are not greater than that of baseline ~~or its equivalent.~~

## 4.5. Section 7.7: Concomitant Therapy

For patients with GPP or EP, methotrexate and oral retinoids will be permitted before and during the study if the patients have been using such medication before starting the study and if doses are not greater than that of baseline. ~~O~~ral corticosteroids and ~~all topical treatment~~ will be

permitted before and during the study, if the patients have been using such medication before starting the study and if average daily doses are not greater than 10 mg/day of prednisone or its equivalent, and Cyclosporine will be permitted until Week 2 (Visit 4), if the patients have been using such medication before starting the study and if daily doses are not greater than that of baseline or its equivalent. For methotrexate, oral retinoids, oral corticosteroids and cyclosporine, dose reductions are allowed but dose increases of these drugs are not allowed during the study. All topical treatment will be permitted before and during the study.

**Table AMAJ(1).2. Excluded Classes of Concomitant Medications or Classes with Restricted Use**

Drug Class	Allowed for Chronic Use	Allowed with Restrictions	Conditions for Allowed Use

Topical treatment for psoriasis or any other skin condition (including but not limited to, corticosteroids, crisaborole, anthralin, calcipotriene, topical vitamin D derivatives, retinoids, tazarotene, pimecrolimus, tacrolimus, emollients and other nonprescription topical products containing urea, >3% salicylic acid, alpha- or beta-hydroxyl acids)
	N	N	
Exception: For patients with GPP or EP, all topical treatments will be permitted. These topical medications should not be used within approximately 12 hours prior to study visits.

Other systemic immunomodulating treatments (for example, MTX, cyclosporine A, corticosteroids, cyclophosphamide)
	N	N	
Exception: For patients with GPP or EP, methotrexate will be permitted before and during the study if doses are not greater than that of baseline, oral corticosteroids will be permitted before and during the study, if average daily doses are not greater than 10 mg/day of prednisone or its equivalent, and cyclosporine will be permitted until Week 2 (Visit 4), if daily doses are not greater than that of baseline. For these treatments, dose reductions are allowed but dose increases are not allowed during the study.

*Systemic immunomodulating treatments (corticosteroids only)
	N	Y	
Limited use of systemic corticosteroid ONLY as needed for limited, short-term medical management of TEAE may be considered. Such drug class might be considered psoriasis therapy if used under other regimens. Limited use during TEAE management is considered to not be consistent with psoriasis therapy. Exception: For patients with GPP or EP, oral corticosteroids permitted if average daily doses are not greater than 10 mg/day of prednisone or its equivalent.

Drug Class	Allowed for Chronic Use	Allowed with Restrictions	Conditions for Allowed Use
Systemic psoriasis therapies (for example, retinoids, fumarates, apremilast)	N	N	Exception: For patients with GPP or EP, oral retinoids will be permitted before and during the study if doses are not greater than that of baseline. For this treatment, dose reductions are allowed but dose increases are not allowed during the study.

Leo Document ID = 6222d326-ace9-457b-b374-ac10dd058be3

Approver: PPD  
Approval Date & Time: 26-Apr-2018 20:56:10 GMT  

 App.2.2. Japan Addendum General Considerations 74

 App.2.3. Japan Addendum Efficacy/Health Outcome Analyses 75

 App.2.4. Japan Addendum Safety Analyses 77

Table of Contents

Table	Page
Table AMAJ.4.1. Protocol-Defined Objectives and Endpoints.....	10
Table AMAJ.6.1. Patient Populations for Analysis	20
Table AMAJ.6.2. Treatment Groups and Comparisons for Each Study Period and Analysis Population.....	20
Table AMAJ.6.3. Definition of Study Period Time Intervals.....	22
Table AMAJ.6.4. Patient Characteristics (and Variables for Subgroup Analysis).....	30
Table AMAJ.6.5. Description and Derivation of Efficacy/Health Outcomes Measures and Endpoints	36
Table AMAJ.6.6. Description of Efficacy/Health Outcomes Analyses.....	50
Table AMAJ.6.7. Summary Tables Related to Adverse Events.....	58
Table AMAJ.6.8. Summaries/Displays/Analysis for Clinical Laboratory Evaluations.....	59

Table of Contents

Figure	Page
Figure AMAJ.5.1. Illustration of study design for Clinical Protocol I6T-MC-AMAJ.....	16
Figure AMAJ.6.1. Graphical approach to control type 1 error rate for Study I6T-MC-AMAJ.	28

Table of Contents

Appendix		Page
Appendix 1.	Study Visit Definition for Psoriasis Symptoms Scale (PSS).....	72
Appendix 2.	Analysis Plan for Japan Addendum.....	73

3. Revision History

Statistical Analysis Plan (SAP) Version 1 was approved prior to any unblinding.

SAP Version 2 was approved after the unblinding to the external safety Data Monitoring Committee (DMC), and prior to the first unblinding to the study team. The changes made to this SAP are as follows:

- updated the Study Objectives and Study Design figure per Protocol Amendment A and B
- updated [Table AMAJ.6.2](#) the treatment group descriptions and [Table AMAJ.6.3](#) the Study Period definition
- modified the study baseline definition to be more conclusive
- updated the details for common risk difference, categorical mixed-model repeated measures (MMRM), tipping point analysis, and as-observed analysis
- modified multicenter studies to be subgroup analyses
- updated the section of adjustment for covariates
- updated the figure of the graphical approach per Protocol Amendment B
- updated the prior psoriasis therapy and others in the table of patient characteristics and variables for subgroup analysis
- included the adverse events (AEs) occurring prior to the first dose for preexisting conditions
- changed the population for treatment compliance to Induction Safety Population
- updated the reporting details of concomitant therapy
- updated [Table AMAJ.6.5](#) and [Table AMAJ.6.6](#) with additional details, including:
 - changed the description of consistent maintenance to be a stability analysis
 - added the details for cumulative time with 90% improvement in Psoriasis Area and Severity Index from baseline (PASI 90)
 - revised the analysis for the Patient's Global Assessment of Psoriasis, and facial psoriasis
 - revised Short Form 36-item Health Survey (SF-36) domain score analysis with the Responder Definition
 - added analysis to EuroQol 5 Dimensions (EQ-5D) dimension scores
 - added details for 16-item Quick Inventory of Depressive Symptomatology (QIDS-SR16) domain derivation
 - updated the time point and added the period for table of description of the analyses
 - added maintenance of PASI 90/PASI 100 response analysis based on responders at Week 16 and Week 24
- updated the interpretation of p-values for safety sections
- added listing of deaths and clarified some AE reporting by preferred term (PT) instead of nested within System Organ Class (SOC)
- updated the details of hypersensitivity analysis
- modified the subgroup analysis

- added the section of analysis for Japan submission and the Appendix of Analysis Plan for the Japan Addendum
- added the section of analysis for Australian submission
- updated the details of early pharmacokinetics (PK) datalock
- updated [Appendix 1](#) to clarify the week/visit mapping
- made other minor typographical corrections and clarifications not affecting content

4. Study Objectives

Table AMAJ.4.1 shows the protocol-defined objectives and endpoints of the study. In addition, the analysis of some non-protocol-defined endpoints is described in Section 6.11 to provide supportive evidence of efficacy.

The estimand (ICH E9 R1) associated with each endpoint/analysis is documented in the following places:

- The population of interest is described in the protocol inclusion/exclusion criteria and in this document in Table AMAJ.6.1 and Table AMAJ.6.6.
- The endpoints/variables are listed in Table AMAJ.4.1, Table AMAJ.6.5, and Table AMAJ.6.6.
- The handling of intercurrent events is summarized in Section 6.3 and Table AMAJ.6.6.
- Population summary measures are described in Section 6.10 and Table AMAJ.6.6.

Table AMAJ.4.1. Protocol-Defined Objectives and Endpoints

Objectives	Endpoints

Primary^{a,b} To assess whether mirikizumab induction dosing is superior to placebo with respect to high levels of clinical response
	
At Week 16:
 
 • Proportion of patients with an sPGA (0,1) with at least a 2-point improvement from baseline • Proportion of patients achieving a $\geq 90\%$ improvement in PASI from baseline (PASI 90)

Major Secondary^{a,b} To assess whether mirikizumab induction dosing is superior to placebo with respect to clinically meaningful response and highest levels of clinical response
 
To assess whether mirikizumab induction dosing is superior to placebo with respect to body surface area (BSA) affected by psoriasis
 
To assess whether mirikizumab induction dosing is superior to placebo with respect to patient-reported outcomes
	
At Week 16:
 
 • Proportion of patients achieving a 75% improvement in PASI (PASI 75) • Proportion of patients achieving a 100% improvement in PASI from baseline (PASI 100) 
At Week 16:
 
 • Proportion of patients with $\leq 1\%$ of BSA with psoriasis involvement 
At Week 16:
 
 • Proportion of patients with a PSS symptoms score of 0 (free of itch, pain, stinging, and burning) in those with a PSS symptoms score ≥ 1 at baseline • Proportion of patients achieving a DLQI total score of (0,1) with at least a 5-point improvement (reduction) from baseline in patients with a baseline DLQI total score ≥ 5

Protocol-Defined Objectives and Endpoints

Objectives	Endpoints

Major Secondary^{a,b}
 
To assess whether mirikizumab induction dosing is noninferior to secukinumab with respect to high levels of clinical response
 
To assess whether 250-mg mirikizumab Q8W and 125-mg mirikizumab Q8W maintenance dosing is noninferior to secukinumab with respect to high and highest levels of clinical response
 
To assess whether 250-mg mirikizumab maintenance Q8W and 125-mg mirikizumab Q8W dosing is superior to secukinumab with respect to high levels of clinical response*
	
At Week 16:
 
 • Proportion of patients with an sPGA (0,1) with at least a 2-point improvement from baseline • Proportion of patients achieving PASI 90 
At Week 52:
 
 • Proportion of patients achieving sPGA (0,1) • Proportion of patients achieving PASI 90 • Proportion of patients achieving PASI 100 
At Week 52:
 
 • Proportion of patients achieving sPGA (0,1) • Proportion of patients achieving PASI 90 • Proportion of patients achieving PASI 100

Other Secondary^b
 
To assess whether mirikizumab induction dosing is superior to placebo with respect to an early, clinically meaningful response
 
To compare mirikizumab to placebo with respect to clinical response and time to clinical response during the induction dosing period, and with respect to patient-reported outcomes during the induction dosing period
	
At Week 4:
 
 • Proportion of patients achieving PASI 75 
At Week 16 and various time points over the first 16 weeks of dosing:
 
 • Proportion of patients achieving PASI 90 • Change from baseline in PPASI total score in patients with palmoplantar involvement at baseline • Change in PSSI total score in patients with scalp involvement at baseline • Change from baseline in NAPSI total score in patients with fingernail involvement at baseline • Change from baseline on the SF-36 physical component summary (PCS) and mental component summary (MCS) • Change from baseline on PatGA of disease severity** • Change from baseline for the WPAI PSO scores (Absenteeism, Presenteeism, Work Productivity Loss, and Activity Impairment) • Change from baseline in QIDS-SR16 total score in those with a baseline QIDS-SR16 total score ≥ 11 • Proportion of patients achieving a DLQI total score of (0,1) with at least a 5-point improvement (reduction) from baseline in patients with a baseline DLQI total score ≥ 5 • Proportion of patients achieving DLQI (0,1) with DLQI baseline score > 1

Protocol-Defined Objectives and Endpoints

Objectives	Endpoints

To compare mirikizumab to secukinumab with respect to clinical response and time to clinical response during the induction dosing period, and with respect to patient-reported outcomes during the induction dosing period
 
To assess whether 250-mg mirikizumab Q8W and 125-mg mirikizumab Q8W maintenance dosing is noninferior to secukinumab with respect to high levels of clinical response
	
At Week 16 and various time points over the first 16 weeks of dosing:
 
 • Proportion of patients achieving PASI 90 
At Week 24:
 
 • Proportion of patients achieving PASI 90 
At Week 52:
 
 • Proportion of patients achieving an sPGA (0)

To assess efficacy of 250-mg mirikizumab Q8W and 125-mg mirikizumab Q8W as compared to secukinumab with respect to clinical response
	
At Week 52 and at various time points during the Maintenance Dosing Period:
 
 • Proportion of patients achieving PASI 90 • Proportion of patients achieving a DLQI total score of (0,1) with at least a 5-point improvement (reduction) from baseline in patients with a baseline DLQI total score ≥ 5 • Proportion of patients achieving DLQI (0,1) with DLQI baseline score >1

Evaluate the pharmacokinetics and pharmacokinetic/pharmacodynamic relationship of mirikizumab
	
 • Clearance and volume of distribution of mirikizumab • Relationship between mirikizumab exposure and efficacy (sPGA and PASI)

Exploratory
 
To evaluate the potential development of antimirikizumab antibodies and their potential relationship with efficacy, TEAEs, and mirikizumab exposure
	
At Week 16 and Week 52:
 
 • Relationship between TE-ADA and efficacy (sPGA and PASI) • Relationship between TE-ADA and TEAEs • Relationship between TE-ADA and mirikizumab pharmacokinetics

Protocol-Defined Objectives and Endpoints

Abbreviations: BSA = body surface area; DLQI = Dermatology Life Quality Index; MCS = mental component summary; NAPSI = Nail Psoriasis Severity Index; PASI = Psoriasis Area and Severity Index; PASI 75/90/100 = $\geq 75\%$ / $\geq 90\%$ / $\geq 100\%$ improvement in PASI from baseline; PatGA = Patient's Global Assessment of Psoriasis; PCS = physical component summary; PPASI = Palmoplantar Psoriasis Severity Index; PSS = Psoriasis Symptoms Scale; PSSI = Psoriasis Scalp Severity Index; Q8W = every 8 weeks; QIDS-SR16 = 16-item Quick Inventory of Depressive Symptomatology; SF-36 = Short Form 36-item Health Survey; sPGA = static Physician's Global Assessment; TE-ADA = treatment-emergent antidrug antibody; TEAE = treatment-emergent adverse event; WPAI PSO = Work Productivity Activity Impairment Questionnaire – Psoriasis.

- a All primary and major secondary endpoint analyses will utilize the multiplicity control technique called “graphical multiple testing procedure” to control the overall family-wise Type I error rate.
- b Note: A “clinically meaningful” response is a PASI 75 response, which represents at least a 75% decrease (improvement) from the baseline PASI score. A “high level” of clinical response is a PASI 90 response, which represents at least a 90% decrease (improvement) from baseline in PASI score, or sPGA (0,1) response, which represents an “almost clear” response. The “highest level” of clinical response is a PASI 100 or sPGA (0) response, which represents complete resolution of psoriasis.
- * This objective is written as it is in protocol amendment (b), but should be updated to “To assess whether 250-mg mirikizumab maintenance Q8W and 125-mg mirikizumab Q8W dosing is superior to secukinumab with respect to high and highest levels of clinical response.”
- ** This endpoint is written as it is in protocol amendment (b), but should be updated to “Proportion of patients achieving PatGA of disease severity of (0,1) with at least a 2-point improvement from baseline in patients with a baseline PatGA ≥ 2 ”.

5. Study Design

